#### **Objectives**

### **Primary:**

The primary objective of the study is to evaluate the long-term safety of TNX-102 SL 5.6 mg taken daily at bedtime over an additional 40 to 52 weeks in patients with PTSD who have participated in a double-blind lead-in P301 or HONOR study. Some patients will have also participated in an initial 12-week open-label extension study (TNX-CY-P303). This will provide at least 52 weeks of TNX-102 SL 5.6 mg exposure data for at least 50 patients.

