3. OVERALL STUDY DESIGN AND PLAN

This is a 40 to 52-week, multicenter, open-label extension study designed to establish long-term safety exposure and to examine the long-term effect with daily bedtime dosing of TNX-102 SL 5.6 mg (2 x 2.8 mg tablets) in patients with PTSD. This study will be conducted at approximately 35 sites in the United States (US).

Patients who have either: (a) completed the double-blind lead-in study (P301/HONOR study), and completed or are active (at the time of study discontinuation) in the 12-week open-label extension study, P303; or (b) are enrolled in the double-blind lead-in study (P301/HONOR study) that has been discontinued due to results of an interim analysis, will be eligible. For Track A patients, this extension study consists of 5 in-clinic visits, including the Screening/Baseline visit and visits after 7, 16, 28, and 40 weeks of treatment (Visits 3-6). There will also be a telephone visit after 2 weeks of treatment (Visit 2) for patients enrolling from the double-blind lead-in study, P301/HONOR. The total treatment duration of this study will be 40 weeks for patients enrolled under Track A criteria, and 52 weeks for patients enrolled under Track B criteria. Therefore, the maximum total duration of continuous treatment with TNX-102 SL could be approximately 64 weeks for those patients assigned to TNX-102 SL in the lead-in HONOR study who then also completed the 12-week open-label extension study P303. For patients enrolling from the open-label extension study, P303 (Track A), there is no need to repeat assessments at Visit 1 for this study, if the patient enrolls and initiates study treatment within fourteen days of completing the 12-week open-label extension study P303. For patients who are active in the double-blind lead-in study, P301/HONOR (Track B), all Baseline procedures and assessments will be completed at Visit 1.

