12. LONG-TERM SAFETY ANALYSES

Protocol: TNX-CY-P306 Page 25 of 36

Final v1.0

Select safety analyses will be conducted on the data collected across Studies TNX-CY-P301, TNX-CY-P303, and TNX-CY-P306 (the "long-term analysis period"). For purposes of clarity, only subjects in the TNX-CY-P306 Safety Population are included in these analyses, except where specified in Section 12.1. The purpose of this set of analyses is to support the long-term safety profile of TNX-102 SL 5.6 mg per day. Certain definitions and analyses in this Section 12 may differ from that of other sections in this SAP.

All analyses will be summarized for the TNX-102 SL group only, except where specified in Section 12.1. For subjects who were treated with placebo in Study TNX-CY-P301, analyses will exclude the subject data from Study TNX-CY-P301 (except to the extent the baseline record may come from Study TNX-CY-P301, as applicable). For purposes of Sections 12.3 and 12.4, baseline is the last assessment prior to dosing with TNX-102 SL for the first time.

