In addition, the incidence of patients with each category of oral cavity TEAEs will be summarized by increments based on the relative start day of the AE compared to first dose of active drug in any study (0-12 weeks, >12-24 weeks, >24-36 weeks, >36-48 weeks, and >48 weeks). Intervals may be changed for more meaningful interpretation based on the actual distribution of the AE data. For each increment, the denominator will be the number of subjects with risk-time extending into that time interval, specifically, with a duration of exposure to TNX-102 SL of at least the lower limit of that increment. For instance, the number of subjects with >12 weeks of exposure would be the denominator for the >12-24 week increment. Duration of exposure is defined in Section 12.5). The last dose date is the last dose date in Study TNX-CY-P306, and the first dose date is the first dose of TNX-102 SL in any study. If a subject experienced more than one TEAE in a given category, the first event will be selected.

A similar analysis will be provided for the incidence of TEAEs and serious TEAEs by SOC and preferred term.

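### The open >48-week interval in the long-term adverse event tables covers about 4 to 16 planned weeks per completer, so its crude percentage is not comparable with those of the 12-week intervals

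*SAP*

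**What the plan says.** SAP 12.2 sets the intervals as "0-12 weeks, >12-24 weeks, >24-36 weeks, >36-48 weeks, and >48 weeks", counted from the first dose of TNX-102 SL in any of the three studies. The denominator is subjects "with a duration of exposure to TNX-102 SL of at least the lower limit of that increment"; the SAP's own example is that "the number of subjects with >12 weeks of exposure would be the denominator for the >12-24 week increment". The method is stated for the oral cavity event categories and then extended to all and to serious treatment-emergent events by system organ class and preferred term. The intervals may be redrawn, but the stated ground is how the events are distributed, not how exposure is.

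Time on drug is fixed by design. SAP 3 gives P306 treatment as "40 weeks for patients enrolled under Track A criteria, and 52 weeks for patients enrolled under Track B criteria" and says that "maximum total duration of continuous treatment with TNX-102 SL could be approximately 64 weeks". SAP 12 adds: "For subjects who were treated with placebo in Study TNX-CY-P301, analyses will exclude the subject data from Study TNX-CY-P301", apart from a baseline record where one is needed. A placebo patient's clock therefore starts with the first open-label dose.

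SAP 12.5 summarizes total exposure, in categories that also end with an open one from 48 weeks. Neither document plans an adverse event rate per unit of time at risk.

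**The concern.** An incidence table by time since first dose invites the reader to look along the row and ask whether events become more or less frequent with longer use. That works only if each column covers about the same observed time per patient. The four closed intervals have equal planned width. The last one has no upper limit, and how long a patient is watched in it depends on the lead-in arm and the entry route.

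This is the period that the extension was run to observe. The Protocol synopsis says of its exposure target: "This will provide at least 52 weeks of TNX-102 SL 5.6 mg exposure data for at least 50 patients". If risk were unchanged over time, the last column could still look lower or higher than the others solely because of how long its patients were followed.

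**Working it through.** **Step 1. The plan's own figure.** Active drug in P301 (12 weeks), completed P303 (12) and P306 under Track A (40): 12 + 12 + 40 = 64 weeks. This reproduces the SAP's approximate maximum.

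**Step 2. Planned weeks in the last interval.** Weeks beyond 48 = total planned TNX-102 SL weeks − 48, for completers without gaps. Routes are from the Methodology section of the Protocol synopsis.

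| Route | Total weeks | Weeks beyond 48 |
|---|---|---|
| Track A: P301 active 12, P303 0–12, P306 40 | 52–64 | 4–16 |
| Track B: P301 active 0–12, P306 52 | 52–64 | 4–16 |
| Track B: P301 placebo, P306 52 | 52 | 4 |
| Track B: P301 placebo, P303 0–12, P306 52 | 52–64 | 4–16 |

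Two qualifications. Visit windows of ±7 days, and a gap of up to 14 days between studies (which last dose minus first dose counts as exposed), can stretch the upper end to about 16 + 2 + 1 = 19 weeks. Also, SAP 3 labels P303 entrants as Track A without regard to P301 arm. On that reading, P301-placebo patients coming from P303 would have 40–52 weeks in total, so 0–4 weeks beyond 48. The two track descriptions need to be reconciled.

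**Step 3. Effect on the percentage.** The documents give no event rate, so assume a constant hazard r, with 1% per week as the central case. The expected percentage with a first event in w observed weeks is 1 − exp(−r·w).

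- 12 weeks: 1 − exp(−0.12) = 11.3%
- 4 weeks: 1 − exp(−0.04) = 3.9%, ratio 0.35
- 16 weeks: 1 − exp(−0.16) = 14.8%, ratio 1.31
- 50:50 mix of 4 and 16 weeks: 9.4%, ratio 0.83
- 75% with 4 weeks: 6.6%, ratio 0.59
- 25% with 4 weeks: 12.1%, ratio 1.07
- Even spread over 4–16 weeks: 1 − [exp(−0.04) − exp(−0.16)]/0.12 = 9.5%, ratio 0.84

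For r from 0.2% to 2% per week, the ratio is 0.34–0.36 at 4 weeks and 1.28–1.33 at 16 weeks, so the result hardly depends on the assumed rate. At 1% per week the distortion cancels when about 32% of patients have 4 weeks and the rest 16.

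**Step 4. The closed intervals.** Suppose the risk over 12 weeks is 10%. If 10%, 20% or 30% of patients leave evenly during the interval, the crude figure becomes 9.5%, 9.0% or 8.5%. That is a smaller effect, and it comes from dropout rather than from the design.

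**Step 5. Does a rate remove the problem?** At 1% per week, with time stopped at the first event, 100 patients give 3.92 events in 392 patient-weeks (4-week window), 11.31 in 1,131 (12 weeks) and 14.79 in 1,479 (16 weeks). Each is 1.0 per 100 patient-weeks.

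**The case against.** The strongest reply is that the SAP plans no comparison between intervals: no test, no trend and no stated conclusion. The tables are descriptive and come in addition to the main event tables. The denominator already drops patients who never reach an interval, the study sequences are tabulated under SAP 12.1, and exposure is summarized under SAP 12.5. Precision will also be low. With 50 patients, the number in the exposure target, 5 events would be 10% with an exact 95% interval of about 3% to 22%, so a shift of two percentage points would not be visible.

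Most of this stands, and it limits the weight of the point. It does not remove it. Counting who enters an interval does not account for time spent in it. The exposure categories are open from 48 weeks too, so they do not show how time beyond Week 48 is distributed. Splitting one event type by time since first dose has little purpose unless the columns are read against each other.

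A reader might infer that late risk will be understated, or that it will be far off in one direction. The documents do not support that. The outer ratios need all patients on one kind of route, intermediate routes exist, and the mix is not given. Nor does it follow that the whole table is unusable: the difficulty that the design creates is confined to the open column.

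**Conclusion.** The point holds for one column and one use. As planned, the percentage for the interval beyond 48 weeks should not be read against the 12-week intervals, because planned completers are observed in it for about 4 to 16 weeks and each counts as one full patient. Under a constant hazard the distortion lies between a factor of about 0.35 and about 1.3, and near 0.83 for a balanced mix or an even spread. These figures assume planned completers without gaps and a hazard that does not change over time. The direction and size in this trial remain open until the route mix is known. All the percentages stay valid as descriptive counts. This is a worthwhile, inexpensive improvement to the SAP, not a flaw that undermines the safety evaluation.

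**What to change.** In SAP 12.2:

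- Keep the percentages. For each interval add the patient-weeks of TNX-102 SL exposure inside it and the rate of first events per 100 patient-weeks.
- End each patient's time at the counted event, the last dose or the end of the interval, whichever comes first.
- State whether the first event is taken per interval or over the whole period; the present text does not say. If over the whole period, take patients with an earlier event out of the time at risk in later intervals. Otherwise they add time but cannot add events.
- Use the rate, not the percentage, for any comparison between intervals, and footnote that the last percentage covers unequal observation.

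Splitting the last interval at Week 52 is not a substitute. Protocol Appendix 1 sets Visit 7 at Day 365 ± 7, with dosing from the evening of Day 0. A punctual direct entrant whose last dose is on Day 364 has 364 − 0 + 1 = 365 days of exposure, against 364 days in 52 weeks. That patient would enter a row beyond Week 52 with about one day observed. Across the visit window the range is 358 to 372 days, so the same defect would return.

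The cost is a few lines of SAP text and additional columns computed from dose and event dates already collected. The rates in the last interval will be imprecise.

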#### **Safety Analyses:**

Safety data will be summarized as a single treatment group receiving 1 or more doses of TNX-102 SL 5.6 mg. Adverse events will be coded using the same version of the Medical Dictionary for Regulatory Activities (MedDRA) as used for the lead-in HONOR study and will be summarized overall and by preferred term and system organ class (SOC). Adverse events will also be summarized by severity and relationship to study drug. Serious AEs and AEs leading to discontinuation of study drug will also be summarized. Adverse events that are ongoing in the 12-week open-label extension study P303 or the lead-in double blind HONOR study will be transcribed into the eCRF. All other adverse events that are reported after starting TNX-102 SL in this extension study, or that worsen after entry into this extension study, will be considered newly emergent AEs (NEAEs), even if the type of event was previously reported (and resolved) during either the HONOR study or the 12-week open-label extension study.

Actual values and change from baseline for clinical laboratory test results, vital sign measurements, depression status via the BDI-II and PTSD symptom status via the PCL-S, will be summarized at endpoint using descriptive statistics (n, mean, SD, median, minimum, and maximum). The number of

<sup>1 Tonmya is the FDA conditionally accepted proposed proprietary name for TNX-102 SL for the treatment of PTSD.

patients with baseline and treatment-emergent suicidal ideation and/or suicidal behavior or self-injurious behavior, based on the C-SSRS, will be summarized by treatment group.

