## For all patients:

- Obtain written informed consent to participate
- Inclusion criteria
- Review and transcribe new concomitant medications as well as those which are to be continued from the double-blind lead-in HONOR study or the 12-week open-label extension study P303
- Review and transcribe new AEs as well as those which are ongoing from the doubleblind lead-in HONOR study or the 12-week open-label extension study P303

For patients enrolling from the double-blind lead-in study, P301/HONOR only (or patients rolling over to study P306 more than 14 days after the final visit of the 12-week open-label extension study P303):

- Obtain vital signs, including weight. The height collected at baseline from the lead-in study will be utilized for body mass index (BMI) calculations in this study.
- Perform a visual exam of the oral cavity
- Have the patient complete the PROMIS-Sleep Disturbance scale and the SDS.
   Review each scale for completeness once done.
- Have the patient complete the BDI-II
- Conduct the C-SSRS after reviewing the results of the BDI-II
- Draw blood for clinical laboratory testing
- Review patient's lifetime psychiatric treatment history, demographic information and medical history to ensure the information recorded during the double-blind lead-in study is accurate and complete, as it will also be included in the extension study's database.

Only those patients meeting all of the inclusion criteria will be eligible to continue.

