10.1 Adverse Events

All AEs will be coded using MedDRA, version 19.0.

Newly emergent adverse events (NEAEs) are defined as any new AE that started after the patient's first dose of study drug in Study TNX-CY-P306, or any unresolved AE first reported in Study TNX-CY-P301 or Study TNX-CY-P303 that exhibited an increase in severity, frequency or relationship after the patient's participation in Study TNX-CY-P306 had begun. For clarity, adverse events are classified as NEAEs based on a negative response to the CRF question "Did the AE start prior to the first dose?".

An AE summary table will be presented for the following:

• NEAEs by severity

Protocol: TNX-CY-P306 Page 21 of 36

Final v1.0

• NEAEs leading to study drug discontinuation

- NEAEs by relationship
- SAEs
- Oral Cavity NEAEs

Summaries of incidence rates (frequencies and percentages) of individual AEs by MedDRA SOC and preferred term will be prepared. Such summaries will be displayed for all NEAEs, NEAEs by maximum severity, NEAEs by strongest relationship to study drug, and oral cavity NEAEs. Incidence of oral cavity NEAEs will be presented by category and preferred term, rather than SOC and preferred term.

Each participant will be counted only once within each summation level (SOC; preferred term). If a participant experiences more than one NEAE within each summation level only, the NEAE with the strongest relationship or the maximum severity, as appropriate, will be included in the summaries of relationship and severity.

Oral cavity adverse events will be defined by a custom MedDRA query (CMQ). These events will be further divided into 4 categories, as follows: 1) Sensory 2) Discomfort 3) Irritation/inflammation and 4) Lesions. Each category will be defined by a CMQ.

Additionally, a summary of the Oral Cavity AE characteristics will be presented; this includes information such as temporal proximity to the dose, duration and whether the AE was present the following morning. For purposes of this summary, only oral cavity NEAEs with the response "Yes" to the CRF question "Is AE in oral cavity"? will be included.

NEAEs pertaining to abuse potential will be reported by SOC and preferred term, and displayed in tabular format. Terms to be included may be found in Appendix 3.

In the AE data listings, all AEs collected in study TNX-CY-P306 will be displayed. AEs that are newly-emergent will be flagged.

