12.2 Long-Term Adverse Events Analyses

For purposes of the long-term AE analyses, treatment-emergent AEs (TEAEs) are any AE with an onset at the time of or following the start of treatment in any of the 3 studies (TNX-CY-P301, TNX-CY-P303, and TNX-CY-P306). To align with the study-level CSR, any AE identified as a TEAE in the study-level CSR for study TNX-CY-P301 will be deemed a TEAE.

Analyses of TEAEs will be presented only for the TNX-102 SL group. Specifically, for subjects who were actually treated with placebo in Study TNX-CY-P301, any TEAEs collected in Study TNX-CY-P301 would be disregarded; only TEAEs that are newly-emergent in Studies TNX-CY-P303 or TNX-CY-P306 would be included. For subjects treated with TNX-102 SL in Study TNX-CY-P301, any AE identified in either the TNX-CY-P303 or TNX-CY-P306 database will be deemed treatment-emergent and eligible for inclusion in analyses, unless the start date is collected and is prior to the treatment start date in TNX-CY-P301.

An overall summary of AEs will summarize the number and percentage of subjects with any TEAE, nonfatal serious TEAE, TEAE leading to death, TEAE by maximum severity, TEAE by maximum relationship, TEAE leading to dose interruption, TEAE leading to dose reduction, TEAE leading to study drug discontinuation, or oral cavity TEAE (see definition below in this section) by category, in the long-term analysis period.

The following analyses of TEAEs will be completed:

Overall summary of TEAEs

Protocol: TNX-CY-P306 Page 26 of 36

Final v1.0

- Incidence of TEAEs by SOC and preferred term
- Incidence of serious TEAEs by SOC and preferred term
- Incidence of TEAEs leading to study drug discontinuation by SOC and preferred term
- Incidence of oral cavity TEAEs by category and preferred term
- Incidence of serious oral cavity TEAEs by category and preferred term
- Incidence of oral cavity TEAEs leading to study drug discontinuation by category and preferred term
- Incidence of TEAEs potentially suggestive of abuse by SOC and preferred term

Oral cavity TEAEs are defined in Section 10.1. TEAEs are identified as potentially suggestive of abuse based on the preferred terms listed in Appendix 3. Of note, somnolence and sedation are known and expected cyclobenzaprine drug effects; these preferred terms will still be included in these displays, if present.

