12.5 Long-Term Exposure

Summary statistics will be presented for duration of exposure (days and weeks) in the long-term analysis period, defined as the [last dose date of TNX-102 SL – first dose date of TNX-102 SL + 1], for TNX-102 SL. Duration of treatment (weeks) will also be summarized as categorical measures (eg, 0-12 weeks, \ge 12 – 24 weeks, \ge 24 – 36 weeks, \ge 36 – 48 weeks, and \ge 48 weeks).

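### SAP 12.2 counts only a subject's first event by exposure increment but keeps that subject in later denominators, so later increments understate interval incidence for common categories

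*SAP*

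**What the plan says.** SAP 12.2 (Long-Term Adverse Events Analyses) plans a summary of subjects with each category of oral cavity TEAE, by start day relative to the first active dose. The increments are 0-12, >12-24, >24-36, >36-48 and >48 weeks.

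- **Numerator.** "If a subject experienced more than one TEAE in a given category, the first event will be selected".
- **Denominator.** Subjects "with a duration of exposure to TNX-102 SL of at least the lower limit of that increment". The SAP's own example uses everyone with more than 12 weeks of exposure as the denominator for >12-24 weeks.
- **Exposure.** SAP 12.5 says "Summary statistics will be presented for duration of exposure (days and weeks) in the long-term analysis period" and defines it as last minus first TNX-102 SL dose date, plus one. It does not end at an adverse event.
- **Category.** SAP 10.1 says of oral cavity events: "These events will be further divided into 4 categories". These are sensory, discomfort, irritation/inflammation and lesions.
- **Extension.** "A similar analysis will be provided for the incidence of TEAEs and serious TEAEs by SOC and preferred term". The SAP does not say whether the first-event rule carries over to these rows.

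**The concern.** The word category belongs to the four oral cavity groups, while the time bins are called increments or intervals. So the numerator rule picks one event per group over the whole long-term period. The denominator rule looks at exposure alone. After a first event a subject can add nothing more to the numerator for that group, but still adds one to the denominator of every later increment reached.

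These are the planned tables of adverse events by duration of exposure, in a section meant to support the long-term safety profile. A reader will use them to judge whether onset changes with time on drug. The rule builds in a downward slope, which is the favourable direction, even when risk is constant. Oral cavity categories are where it matters most, because the groups are broad and the product is sublingual.

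**Working it through.** The plan states no event rate, event duration or stopping rate, so there is no figure of its own to reproduce. All rates below are assumptions.

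**Model.** At the start of each 12-week increment, subjects on drug are N (no event yet), R (earlier event resolved) or O (event ongoing). Subjects in N and R start an event with probability p. A fraction s of these then stop drug. Of the rest, a fraction q have an event that persists to the end.

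- SAP rule: pN/(N+R+O)
- Once per increment over all exposed: p(N+R)/(N+R+O)
- First occurrence over event-free subjects: pN/N = p

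**Nobody stops drug (s = 0).** N = (1-p)^(k-1) in increment k and N+R+O = 1, so the SAP rule shows p(1-p)^(k-1). With p = 10% and 200 subjects (the planned maximum in Protocol 6.2):

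| Increment (weeks) | First events | SAP denominator | SAP rule | Event-free denominator | First occurrence |
|---|---|---|---|---|---|
| 0-12 | 20.0 | 200 | 10.0% | 200 | 10.0% |
| >12-24 | 18.0 | 200 | 9.0% | 180 | 10.0% |
| >24-36 | 16.2 | 200 | 8.1% | 162 | 10.0% |
| >36-48 | 14.6 | 200 | 7.3% | 145.8 | 10.0% |

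In the fourth increment the SAP rule gives:

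- p = 1%: 0.01 × 0.99³ = 0.97%
- p = 5%: 0.05 × 0.95³ = 4.29%
- p = 10%: 0.10 × 0.90³ = 7.29%
- p = 20%: 0.20 × 0.80³ = 10.24%

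Drop-out unrelated to events scales numerator and denominator alike. A simulation with 10% drop-out per increment (p = 10%, q = 0.5) again gave 10.0, 9.0, 8.1 and 7.3%.

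**Size of the gap, by comparator.** Against first occurrence over event-free subjects, the fourth-increment gap at s = 0 is p - p(1-p)³ whatever the persistence: 0.7, 2.7 and 9.8 points at 5, 10 and 20%. Against once-per-increment counting over all exposed, persistence matters, because a subject with an ongoing event cannot start a new one. That count is p(1-pq)³, so the gaps are:

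| p | q = 0 | q = 0.5 | q = 1 |
|---|---|---|---|
| 5% | 0.7 | 0.35 | 0 |
| 10% | 2.7 | 1.3 | 0 |
| 20% | 9.8 | 4.3 | 0 |

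**Half stop drug after an event (s = 0.5, p = 10%).** For q = 0, 0.5 and 1 the SAP rule gives 8.50, 8.47 and 8.43%. Once-per-increment counting gives 10.00, 9.19 and 8.43%. The gaps are 1.5, 0.7 and 0 points. If all stop (s = 1), R and O are empty and the gap is 0 against either comparator.

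**Unequal risk between subjects.** Take a beta distribution with mean 10% and coefficient of variation 1, so a = 0.8 and b = 7.2. First occurrence in increment k is 0.8/(8 + k - 1), which gives 10.0, 8.9, 8.0 and 7.3%. Multiplying by the proportion still event-free gives the SAP rule: 10.0, 8.0, 6.6 and 5.5%.

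The open-ended >48-week increment is not quantified.

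**The case against.** **The rule can be read as a first-onset distribution.** First onsets over everyone exposed is a definable quantity, too low only if taken as interval risk. That is true. But the SAP calls the table incidence, justifies the denominator by time at risk, and does not label it as first occurrence.

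**First may mean first within an increment.** That reading would remove the mismatch, but it is not stated. The count-once rule in SAP 10.1 names only SOC and preferred term as levels. SAP 10.3 shows that the authors specify counting per visit or time frame when they want it.

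**The size is assumed and depends on the comparator.** This stands. No rates are given, and the gap can be zero.

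**The simple fix is only a partial cure.** Also true. In the unequal-risk example the SAP rule falls 4.5 points over four increments and first occurrence still falls 2.7.

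**The displayed trend may not be favourable overall.** SAP 12 limits these tables to subjects dosed in P306, which can lower the early increments. The net slope could go either way. That is a separate problem and does not correct this one.

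**The tables are descriptive and supplementary.** No test is attached, and both the overall long-term tables in SAP 12.2 and the P306 NEAE tables in SAP 10.1 are unaffected. This limits the weight of the point but does not remove it.

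**Conclusion.** The concern holds on the plain reading of SAP 12.2. The numerator is restricted to first events and the denominator is not restricted to subjects who can still have one, so later increments of common categories are biased downward as interval incidence. At an assumed constant 10% risk per increment, with everyone on drug, >36-48 weeks reads 7.3%. At 1% the effect is negligible, and so it is for most serious TEAEs. SOC and preferred-term rows are affected only if the similar analysis uses the same rule. The result assumes that at least some subjects stay on drug after an event. This should be fixed before the tables are produced; it does not threaten the study's main safety summaries.

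**What to change.** State in SAP 12.2 whether first means first overall or first within each increment, make the denominator match, and say whether the rule covers the SOC and preferred-term tables. Two options work.

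**(a) First occurrence (simpler).** Keep first events, remove from later denominators any subject with an earlier event of that category, SOC or preferred term, and label the table as first occurrence. This takes one or two sentences and minor programming. Event duration and later duplicate records do not affect it. At 10% equal risk, with everyone on drug, >36-48 weeks moves from 7.3% to 10.0%. A footnote should say that unequal risk between subjects can still produce a decline.

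**(b) Once per increment.** Count each subject once in every increment in which a new TEAE starts, over exposed subjects. This also applies if a within-increment rule was intended. It needs three further rules:

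- Merge records of one episode across P301, P303 and P306, using the original start date. Protocol 9.1.5 tells sites to "Review and transcribe new AEs as well as those which are ongoing from the doubleblind lead-in HONOR study", and the Protocol synopsis says that events ongoing in P303 "or the lead-in double blind HONOR study will be transcribed into the eCRF". For subjects on active drug in P301, SAP 12.2 adds that "any AE identified in either the TNX-CY-P303 or TNX-CY-P306 database will be deemed treatment-emergent and eligible for inclusion in analyses", unless a recorded start date precedes P301 treatment. As an illustration with p = 10% and q = 0.5, 1 - 0.95² = 9.75% of subjects have an ongoing event at about week 24, when a Track A subject enters P306. If one in ten of these were re-recorded with a later start date (an assumption), >24-36 weeks would read 9.03 + 0.98 = 10.0% instead of 9.0%.
- State which date applies to an event counted because it worsened.
- Exclude from an increment's denominator subjects whose event of that type is ongoing throughout it, or footnote this. Without the exclusion, >36-48 weeks at 10% reads 10.0, 8.6 or 7.3% if none, half or all events persist.

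Option (b) costs somewhat more, because records must be matched across three databases. Neither option needs new data. The price of both is that late percentages will generally look somewhat less favourable.
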